Aim 2: We will rate training fidelity via two constructs: (1) content and (2) coverage^{41,42} during the week-long training session and community-based outreach sessions (Appendix 2). Understanding the fidelity of training delivery is essential to interpreting the effect of the intervention on PPE behavior change. If HCW + healer teams can deliver training with greater or equal fidelity than HCWs alone, PPE training can be more quickly scaled up nationwide (given the large number of healers) and conducted at lower cost (healers charge considerably less per hour than HCWs). We believe that the healer + HCW teams may have more motivation to deliver the program with fidelity during community-based sessions than the team of HCWs alone because of healers' desire to protect their peers living in their own community. Three HCWs who volunteer to work on this project will be randomly assigned to the intervention team (along with the healers), with six volunteer HCWs assigned to the control arm.

Aim 3: Healers will complete an interviewer-assisted survey immediately post training (Appendix 3) using the Consolidated Framework for Implementation Research framework⁴³ (compatibility of PPE with current behavior, peer pressure to use PPE, perception of the inclusiveness of the training process, cost) and individual characteristics from the situated-IMB model (Figure 3)^{44,45}. During the six months of the trial, healers in each arm will record data on our primary outcome: the proportion of injections conducted using PPE in two ways.

(1) Collect used sharps and PPE. Healers will be given containers to place all used gloves and razors/sharps to both ensure healer safety and allow us to count materials used (healers use gloves and a single razor once per patient and subsequently throw them into latrines or trash piles). We will use the *number of glove pairs as the numerator* (number of times they used gloves during procedures) and the *number of razor blades as the denominator* (number of injections given). While some may be concerned with social desirability bias, healers have been told for years to use gloves and were very open with us about their non-use. Healers have no reason to

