Aims 2 & 3: Traditional healers randomized to both the control and intervention arms will receive PPE education and training, general HIV prevention education and skill building (including condom use, positive prevention, and pre-/post-exposure prophylaxis services), and three educational outreach and coaching visits at the healer's place of practice to provide on-the-ground advice and support for PPE use. These training and educational outreach sessions are designed to allow healers to receive education about bloodborne disease transmission (information), accurately assess their risk of contracting bloodborne illness (motivation), and develop skills to effectively don, doff, and dispose of used PPE (behavior) (Appendices 2 and 3). Outreach visits will focus on delivering five key messages and troubleshoot any issues healers may have in following recommendations. We will assess the impact of our evidence-based PPE intervention on the knowledge, motivation, and behavioral skills developed by traditional healers using the Situated Information Motivation and Behavioral Skills (Situated-IMB) model.⁴⁴ The use of in-class

and educational outreach strategies have yielded improvements in clinical care delivery,⁴⁶⁻⁴⁸ including use of PPE,⁴⁹ among physicians, nurses, and community health workers in low-resource settings. These strategies were selected in consultation with traditional healers in Agincourt who reported never having received training on how to protect themselves from exposures based on the strategies used around the world to train health care providers to avoid infection.^{33,36,49-51} PPE use is feasible and acceptable to most healers and their patients already,²⁷ but they lack the knowledge and/or motivation to use gloves properly and regularly.

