Our intervention arm will receive the same training and educational outreach as the control arm, but with training and outreach conducted by a clinical team that includes healers who adopted and use PPE on their own (early adopters).³⁷⁻⁴⁰ Early adopters are people who identify a new behavior as innovative (i.e. use of latex gloves) and adopt this behavior before the majority of their colleagues. Used primarily in the Diffusion of Innovation Theory⁵² to explain adoption of new behaviors, we hypothesize that the strategy of engaging early adopting healers as trainers in collaboration with HCWs will increase peer pressure, perceived tension for change, participant self-efficacy, and acceptability of PPE use among healers who do not use any barrier to blood exposure. Early adopters can achieve this by highlighting relative advantages, compatibility with their role of a traditional healer and leader in the community, simplicity, and ease of trialability of using gloves with patients.⁵²

Participants will receive a baseline and end line (7 months post- training) HIV test (to detect any seroconversion events and to determine if those living with HIV are as motivated to use PPE as those who are HIV-negative). Participants will also complete baseline and end line surveys to assess their knowledge, motivation, and behavioral skills to determine the impact of training on the healer. Once a month, a study assistant will visit each healer to collect all used sharps and PPE; three times during the study the study assistant will also conduct observations of healers using PPE to determine if they are using it correctly post-training.

Healers and healer care workers who are selected, consent and contribute to the training of healers will be reimbursed for their transportation to the training venue and provided with a small token of appreciation (a voucher to a local store for R150) at the conclusion of the workshops.

6. Study Location

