Analysis plan for coverage: We will calculate the percentage of sessions completed as the actual number of sessions completed for a participant divided by the total number of planned sessions. The percentage of sessions completed between the two intervention arms will be compared using mixed effects Poisson regression with the number of planned sessions (in most cases 3) as an offset. 95% confidence intervals will be constructed. The models will include random effects for the trainers. Covariates will include patient volume, sex, and baseline age. Missing data and LTFU will be handled as described above.

Aim 3: The analysis will follow intent-to-treat protocol. Our primary outcome is the proportion of a healer's procedures that were conducted using latex gloves (numerator = number of procedures with blood exposure, denominator = number of procedures). We will compare the blood exposure proportions between the two study arms using a negative binomial regression model. In the negative binomial regression, the outcome will be the number of times gloves were used and the number of procedures performed by the healer (number of razor blades) will be included as an offset. Such an analysis is appropriate because it properly accounts for heterogeneity between healers in the number of procedures performed, and the resulting estimates from the model can be interpreted as relative proportions (proportion of procedures with blood exposure in Arm 1 vs. proportion of procedures with blood exposure in Arm 2). In addition to our primary intervention

exposure variable, we will include healer sex and baseline age as covariates in our model. Sensitivity analyses will compare blood exposure proportions between the two intervention arms using a two-sample t-test; a Wilcoxon rank sum test will be fit as needed to avoid normality assumptions.

Based on prior experience working with healers, we anticipate very low rates of loss to follow-up (LTFU). Healers who are LTFU will be censored at the time of their last recorded data collection, and inverse-probability of censoring weights based on healer characteristics randomization will be used, if necessary, to account for differences between healers who are LTFU and those who remain in the study. Missing data will be imputed using chained equations and 20 imputation replications.

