The secondary outcome, proportion of injection events, will be analyzed in a manner identical to that of our primary outcome except the outcome will be the total number of skin-cutting events performed by the healer, regardless of the use of PPE. A negative binomial regression model will be fit using the number of overall procedures as an offset. While we will not specifically look at HIV seroconversion as a study outcome, we will assess healers' baseline and end line HIV status for ethical reasons. Historical data show that the one-year incidence rate of HIV seroconversion is 1.7%. Since the incidence rate is low, we will likely not have adequate power to see a difference between intervention arms, but this information will allow us to appropriately power our subsequent R01 trial.

A separate analysis will assess each strategies' effect on PPE self-efficacy, PPE knowledge/skills, and accurate risk assessment post-training. We will explore whether the intervention effects on these measures differ by a) trainer fidelity to the intervention and/or trainer identity (healer vs. clinician), respectively. These analyses will provide quantitative data to revise and refine, as needed, the intervention for evaluation in a large RCT effectiveness study as a means of improving prevention engagement while reducing stigma.

8. Ethical Considerations

Recruitment and Consent

Aim 1: *Traditional healers* from the target community will be recruited via two strategies: (1) Healers in target catchment area are currently being mapped by two students (one from Vanderbilt and one from University of Witwatersrand). The healers are providing their address/location and contact information (phone numbers, contact for other family members) for use in future activities (including research endeavors). The healers will be contacted and given general information about the proposed study. All healers will be invited to community meetings where more information about the study procedures and aims will be provided. (2) The Kukula Traditional Healers association- the primary healer organization in the region- will hold 3 meetings to recruit healers interested in participating. Healers who express interest will be given the option for dates/locations where we will conduct recruitment fairs or the option to have a study assistant visit them at home. All recruitment will be conducted in a private room or at the home of the healer (as per the participants preference).

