3. Finally, any associated materials such as medical record notations or reports with the name and medical record number of the individual redacted (removed) will be included with the report.
4. When applicable, a "Request for Amendment" indicating changes associated with the event or problem is submitted.

Serious Adverse Event (SAE) Reporting

The Division of AIDS Table for Grading the Severity of Adult and Pediatric Adverse Events (DAIDS AE Grading Table), Version 1.0, December, 2004, will be used to determine clinical and laboratory grades of any/all grade 2 or higher events (including signs and symptoms, laboratory abnormalities, and diagnoses).

In addition, any/all deaths, disabilities, malignancies, and/or any other conditions deemed serious and/or debilitating/incapacitating by the clinical team will be reported to all involved ethical review boards. The PI will submit SAE information as required by local regulatory or other local authorities, and the research team will adhere to these stringent requirements and submit full reports detailing any SAEs in a timely fashion (i.e. in accordance with existing standards). After the end of the protocol-defined SAE reporting period stated above, the site will report serious, unexpected, clinical suspected adverse drug reactions if the study site staff becomes aware of the event on a passive basis, i.e., from publicly

Benefits

Traditional healers in this study could potentially benefit from PPE education and skill building and increased engagement with the health system which will likely highlight the importance of protecting themselves from blood exposures. Health care workers in this study could potentially benefit from their additional PPE education and skill building, which could help protect themselves from blood exposure.

9. Limitations

This study will not be powered to assess seroconversion among traditional healers exposed to HIV but will give us proxy outcomes (blood exposure) and implementation outcomes (acceptability, fidelity to PPE use) to predict the success if we developed a larger trial.

10. Dissemination Plan

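### Aim 3 models glove use but reports it as blood exposure, and the planned in-practice checks of correct glove use are named in no analysis

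*Combined protocol and SAP*

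**What the plan says.** **Primary outcome.** Section 5 (Measurement of Results, Aim 3) takes glove pairs in the container as the numerator, explained as the "number of times they used gloves during procedures", and razor blades as the denominator. Section 7 (Data Analysis, Aim 3) agrees at first: "Our primary outcome is the proportion of a healer's procedures that were conducted using latex gloves". The parenthesis that follows, however, defines the numerator as procedures in which the healer was exposed to blood. The text goes on: "We will compare the blood exposure proportions between the two study arms using a negative binomial regression model". It then specifies glove uses as the modelled count and razor blades as the offset, and says the estimates can be read as the ratio between arms of the proportion of exposed procedures.

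**Correct use.** Section 5 (Study Procedures, Aims 2 & 3) says of healers that "they lack the knowledge and/or motivation to use gloves properly and regularly". It adds that, on three occasions, the "study assistant will also conduct observations of healers using PPE to determine if they are using it correctly post-training". The analyses for Aims 2 and 3 give these observations no endpoint, score or model. The closest item is a separate analysis of each strategy's "effect on PPE self-efficacy, PPE knowledge/skills, and accurate risk assessment post-training", with no data source or model stated. The skills checklist in Appendix 4 is headed as done when training ends, not in practice. Section 9 lists fidelity to PPE use among the implementation outcomes but does not define it.

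**The concern.** Aim 3 asks about exposure to patient blood, and the container count is a proxy for it. The count records how regularly gloves are worn and carries no information on whether they are worn properly, although the protocol names both as deficits. Calling the estimate a blood-exposure ratio has two consequences. First, the numerator definition and the modelled count point in opposite directions, so a reader who follows the label literally would take more gloves to mean more exposure. Second, even with the direction sorted out, the exposure reading assumes that every gloved procedure is protected. The arms differ in who teaches donning and doffing, so correct use could differ between them. The observations that could show this have no stated place in the analysis.

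**Working it through.** **1. The plan's own figure.** Inputs from section 4 are 61 healers per arm, a difference of 0.20, SD 0.39 and alpha 0.05. A two-sided two-sample t-test needs 60.67, so 61 per arm, and gives 80.22% power, as in Table 1. All nine rows reproduce, so the sample-size calculation is not at fault.

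**2. What the model estimates.** With log(blades) as offset, the exponentiated arm coefficient is the ratio of glove uses per blade. With the plan's example:
- glove-use ratio: 0.4 / 0.2 = 2.0
- ungloved ratio: (1 - 0.4) / (1 - 0.2) = 0.60 / 0.80 = 0.75

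The second cannot be read off the first without the underlying levels. With 0.39 (the preliminary mean) and 0.59 (that mean plus 0.20), the glove-use ratio is 0.59 / 0.39 = 1.51 and the ungloved ratio is 0.41 / 0.61 = 0.67. The absolute difference is 0.20 on either scale, so calling the outcome glove use leaves the power calculation unchanged.

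**3. What a blood-exposure ratio would need.** Let g be the glove-use proportion and c the share of gloved procedures with correct use. If incorrect use counts as exposed, the exposed proportion is 1 - g × c. The documents give no c, so the values below are assumptions. Taking incorrect use as no protection is the extreme case.

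| c, higher-glove arm | c, lower-glove arm | Exposed proportions | Ratio |
|---|---|---|---|
| 1.0 | 1.0 | 0.60 / 0.80 | 0.75 |
| 0.9 | 0.9 | 0.64 / 0.82 | 0.78 |
| 0.7 | 0.7 | 0.72 / 0.86 | 0.84 |
| 0.7 | 0.9 | 0.72 / 0.82 | 0.88 |
| 0.5 | 0.9 | 0.80 / 0.82 | 0.98 |

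Equal c leaves the ratio of protected proportions at 2.0 but moves the exposure ratio towards 1. The order of the arms reverses only if c in the higher-glove arm is below 0.2 / 0.4 = 0.50 of c in the other arm, or below 0.39 / 0.59 = 0.66 for the second pair of levels.

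**4. What the observations could show.** Three observations on each of 61 healers give at most 61 × 3 = 183 per arm. Assume 70% correct, a within-healer correlation (ICC) of 0.1 to 0.5 and design effect 1 + 2 × ICC. The effective n is then 183 / 1.2 = 152.5 down to 183 / 2 = 91.5. The 95% half-width for the arm difference, 1.96 × sqrt(2 × 0.7 × 0.3 / n), is 10 to 13 points.

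That needs a gloved procedure at every visit. If gloves are worn at the example rates, the gloved observations number 183 × 0.4 = 73 and 183 × 0.2 = 37. The half-width is then 1.96 × sqrt(0.21 / 73 + 0.21 / 37) = 18 points before any clustering.

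**The case against.** The strongest defence is that the trial is about glove use throughout. The Aim 3 hypothesis, the effect size used for power and the modelled count all concern gloves, so blood exposure may be no more than loose labelling. That is largely right, and it is why correcting the label removes most of the problem.

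A reader might infer that correct use enters no between-arm analysis at all. The documents do not support this. The skills analysis in section 7 refers to the post-training period, as does the description of the observations, and it does not cite Appendix 4, so it could draw on them. The observations might also serve the quality assurance metrics mentioned under Aim 1. What can be said is that no analysis names them.

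A reader might also infer that an arm wearing more gloves incorrectly will be reported as less exposed. That is possible but not shown. It depends on resolving the numerator contradiction in favour of glove use, and distortion of the glove-use comparison requires correct use to differ by arm. Both arms receive the same training content and both teams include HCWs. A glove that is fitted or removed wrongly may still block blood during the procedure.

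Finally, it is tempting to say that the observations suffice to detect an important difference. Step 4 of the working does not support that. Three observations for every healer is itself a reading of the text, and the number with gloves on may be far below 183 per arm.

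**Conclusion.** The point stands as a mismatch between estimand and label, together with a specification gap. As written, section 7 attaches a blood-exposure interpretation to a glove-use model. In the plan's own example, the model's ratio is 2.0 and the non-use ratio is 0.75, and neither measures exposure unless every gloved procedure is protected. This conclusion needs no assumption about correct use. The further effect of incorrect or unequal use is of unknown size: the ratios from 0.78 to 0.98 illustrate assumed rates and are not evidence of bias in this trial. Leaving the in-practice observations unassigned is mostly missing detail. It matters because they are the planned in-practice check on the step from gloves to protection.

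**What to change.** 1. In section 7, Aim 3, define the primary result as the ratio of glove use (glove pairs per razor blade) between arms. Reconcile the numerator definition with the modelled count and remove the blood-exposure interpretation. Apply the same wording to the t-test and Wilcoxon sensitivity analyses and to the description of the differences in Table 1. This costs a few sentences and leaves the model and sample size unchanged.

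2. Add a secondary analysis of the in-practice observations: correct use (yes/no) among observed gloved procedures, compared between arms with a model that clusters on healer, such as a logistic GEE, and adjusts for the Aim 3 covariates (sex and baseline age). Report the difference with its 95% CI beside the primary result. State whether the same data also feed the skills analysis.

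3. Fix a simple correct/incorrect scoring rule before the data are seen, since the documents contain no in-practice scoring form. State that being observed may improve technique and that gloved observations may number well below 183 per arm.

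4. Treat any estimate that multiplies glove use by correct use as exploratory. Its correct-use denominator must be gloved procedures only, or non-use is counted twice.

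Items 2 to 4 cost a short scoring form, one paragraph and one model on observations already planned, plus one more secondary result that will probably be imprecise.

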6.1 Location

The MRC/Wits Agincourt Research Unit oversees the maintenance and operation of the Agincourt Health and Demographic Surveillance Site (HDSS). Roughly 500km northeast of Johannesburg, the unit has been engaged in population-based health and demographic research since 1992. Strong ties with the local community ensure the continual functioning and sustainability of the research.

Constituting a sub-district of the Bushbuckridge district, the Agincourt study site consists of 420 km² of semi-arid scrubland with low rainfall, poorly-suited for subsistence farming though used for game farming and low- density cattle rearing. The study area contains six government run clinics, a private community health centre, and one larger area public health centre with patients being referred to three district hospitals, each located at 25- 55 kilometers from the site and relying on namely public means for transport.

6.2 Study Population

The Agincourt HDSS population is comprised of roughly 120,000 individuals- mainly xiTsonga-speaking- spread throughout 20,000 households in 31 research villages. Roughly one-third of the

permanent HDSS population is comprised of former Mozambican refugees, who immigrated to South Africa during the 1980s. Our population of focus will include traditional healers living in this region, their patients, and health care workers providing services at local health facilities.

7. Data Management and Analysis

Data Management

Qualitative Data: Data from interviews will be transcribed in the original language and subsequently translated into English (if necessary). We will randomly select 10% of the original interviews to be re-translated to check for accuracy. The English transcriptions will be imported into Atlas Ti © to be coded by [name]. All data will be password protected to ensure confidentiality. Data will be stored in restricted access folders (protected by an additional password) that sits on the Agincourt and Vanderbilt servers. Both servers have daily backups scheduled; therefore, all data will be backed up on a day-to-day basis.

The original recordings, which will not include participant names or other identifiable information, will be locked in a file cabinet at the Agincourt field site until they have been entered into the database and the data has been checked for errors. After this point they will be erased to ensure voices cannot be linked back to the transcripts. All paper copies of transcripts will be destroyed once they have been typed up, verified, and electronic versions sent to Vanderbilt. All electronic copies of transcripts will be kept in a password-protected folder on a secure server at Agincourt and Vanderbilt for a period of 7 years, after which time they will be destroyed by the study investigators.

Quantitative data:

Questionnaires, observations of training, as well as HIV testing data will be collected and uploaded to a REDCap database which is housed at Vanderbilt University. REDCap provides automated export procedures for seamless data downloads to Excel and common statistical packages (SPSS, SAS, Stata, R), as well as a built-in project calendar, a scheduling module, ad hoc reporting tools, and advanced features, such as branching logic, file uploading, and calculated fields. It also provides additional security options, including the ability to restrict a user's ability to download data tagged as identifiers to further protect participant privacy.

Study participants will be assigned a unique, coded identification number at the time of study enrolment. In order to maintain participant confidentiality, all laboratory specimens, study case report forms, and reports will be identified using that coded number. Only research staff will have access to the coded number. Key study personnel, including Drs. [name] and [name], will store research data, including medical and laboratory records, in locked cabinets and all e-files will be password protected. Data will be stored in password-protected files within secure buildings at the MRC/Wits Agincourt Research Unit's rural field offices. We have additional measures to enhance security when data are housed at Vanderbilt. Access to all data will be ID and password-protected, including data warehouse software and computers managing and analyzing survey data. No data will be released with any information that may directly or indirectly identify participants, their clinical information, or laboratory results to outside agencies.

Data Analysis

Aim 1: Audio files will be transcribed by a research assistant. The PI will code and analyze the interviews using Atlas-Ti software. Framework analysis will be used to identify responses to our questions about the drivers, core facilitators, and barriers to intervention acceptability and success.⁵³ Two code maps will be developed to categorize data: (1) To understand the social, structural, and informational drivers, facilitators, and barriers to acceptability of education and PPE skill building, and (2) To understand participant concepts of "best practice" for healer PPE

use (including best practice for communicating this use to patients). Data will be coded by two independent coders to ensure that Cohen's Kappa is >85%. For quantitative surveys, results will be summed to generate three scores (acceptability, appropriateness, and feasibility). Descriptive analyses will be done with survey results from each permutation of the intervention to determine if changes made have resulted in improvements. We will triangulate qualitative and quantitative data to ensure understanding; inconsistencies in findings will be investigated to ensure understanding.

Aim 2: Analysis plan for content: A numeric scale will be used to assess the fidelity of the delivery of *each* topic in the training session. Topics include: (1) Delivered information about the definition of PPE, (2) Provided information about when to use PPE, (3) Provided information about what types of PPE to use in different circumstances, (4) Provided information about the appropriate fit of PPE, (5) Provided do's and don'ts of glove use, (6) Provided information about don PPE, (7) Provided information about how and where to remove PPE, (8) Provided information about how to safely store used PPE, (9) Provided information about hand hygiene, (10) Provided instruction and feedback during PPE practice session. Each of the ten training items will be scored (each with a score of 0-10; 10 represents the greatest fidelity to the training guide, 0 not covering the material at all) for a total of 100 points. The summation of all scores across topics will be used to measure fidelity to content for that training session. Each participant will participate in three training sessions. The mean difference between the two interventions in the total fidelity scores will be estimated using mixed effects linear regression models with 95% confidence intervals (CIs). These models will include random effects for the participant (to account for correlation across multiple sessions) and the trainer (to account for one trainer instructing multiple participants) and a 95% CI will be constructed. The outcome will be transformed as necessary to meet modeling assumptions. Covariates will include patient volume, sex, and baseline age. Any missing data will be imputed using chained equations with 20 imputation replications. Based on prior experience working with healers, we anticipate very low rates of loss to follow-up (LTFU). Healers who are LTFU will be censored at the time of their last recorded data collection, and inverse-probability of censoring weights based on healer characteristics randomization will be used, if necessary, to account for differences between healers who are LTFU and those who remain in the study.

Analysis plan for coverage: We will calculate the percentage of sessions completed as the actual number of sessions completed for a participant divided by the total number of planned sessions. The percentage of sessions completed between the two intervention arms will be compared using mixed effects Poisson regression with the number of planned sessions (in most cases 3) as an offset. 95% confidence intervals will be constructed. The models will include random effects for the trainers. Covariates will include patient volume, sex, and baseline age. Missing data and LTFU will be handled as described above.

Aim 3: The analysis will follow intent-to-treat protocol. Our primary outcome is the proportion of a healer's procedures that were conducted using latex gloves (numerator = number of procedures with blood exposure, denominator = number of procedures). We will compare the blood exposure proportions between the two study arms using a negative binomial regression model. In the negative binomial regression, the outcome will be the number of times gloves were used and the number of procedures performed by the healer (number of razor blades) will be included as an offset. Such an analysis is appropriate because it properly accounts for heterogeneity between healers in the number of procedures performed, and the resulting estimates from the model can be interpreted as relative proportions (proportion of procedures with blood exposure in Arm 1 vs. proportion of procedures with blood exposure in Arm 2). In addition to our primary intervention

exposure variable, we will include healer sex and baseline age as covariates in our model. Sensitivity analyses will compare blood exposure proportions between the two intervention arms using a two-sample t-test; a Wilcoxon rank sum test will be fit as needed to avoid normality assumptions.

Based on prior experience working with healers, we anticipate very low rates of loss to follow-up (LTFU). Healers who are LTFU will be censored at the time of their last recorded data collection, and inverse-probability of censoring weights based on healer characteristics randomization will be used, if necessary, to account for differences between healers who are LTFU and those who remain in the study. Missing data will be imputed using chained equations and 20 imputation replications.

The secondary outcome, proportion of injection events, will be analyzed in a manner identical to that of our primary outcome except the outcome will be the total number of skin-cutting events performed by the healer, regardless of the use of PPE. A negative binomial regression model will be fit using the number of overall procedures as an offset. While we will not specifically look at HIV seroconversion as a study outcome, we will assess healers' baseline and end line HIV status for ethical reasons. Historical data show that the one-year incidence rate of HIV seroconversion is 1.7%. Since the incidence rate is low, we will likely not have adequate power to see a difference between intervention arms, but this information will allow us to appropriately power our subsequent R01 trial.

A separate analysis will assess each strategies' effect on PPE self-efficacy, PPE knowledge/skills, and accurate risk assessment post-training. We will explore whether the intervention effects on these measures differ by a) trainer fidelity to the intervention and/or trainer identity (healer vs. clinician), respectively. These analyses will provide quantitative data to revise and refine, as needed, the intervention for evaluation in a large RCT effectiveness study as a means of improving prevention engagement while reducing stigma.

8. Ethical Considerations

Recruitment and Consent

Aim 1: *Traditional healers* from the target community will be recruited via two strategies: (1) Healers in target catchment area are currently being mapped by two students (one from Vanderbilt and one from University of Witwatersrand). The healers are providing their address/location and contact information (phone numbers, contact for other family members) for use in future activities (including research endeavors). The healers will be contacted and given general information about the proposed study. All healers will be invited to community meetings where more information about the study procedures and aims will be provided. (2) The Kukula Traditional Healers association- the primary healer organization in the region- will hold 3 meetings to recruit healers interested in participating. Healers who express interest will be given the option for dates/locations where we will conduct recruitment fairs or the option to have a study assistant visit them at home. All recruitment will be conducted in a private room or at the home of the healer (as per the participants preference).

Health care workers from the target community will be recruited if they provide primary care or HIV/TB services in the primary health care facility. A list of eligible providers will be elicited from the facility manager; three meetings to discuss the study will be held in the clinic. If the health

care worker is interested in participating, they will be consented by a study assistant at the health facility or in a location of their preference.

Aims 2 and 3: Traditional healers (participants) from the target community will be recruited via two strategies: (1) Healers in target catchment area are currently being mapped by two students. The healers are providing their address and contact information (phone numbers, contact for other family members) for use in future activities (including research endeavors). The healers will be contacted and given general information about the proposed study. All healers will be invited to community meetings where more information about the study procedures and aims will be provided. (2) The Kukula Traditional Healers association will hold 3 meetings to recruit healers interested in participating. Healers who express interest will be given the option for dates/locations where we will conduct recruitment fairs.

Traditional healers (trainers) from the target community will be recruited based on results of a previous PPE use study among 200 healers. These healers have given us permission to contact them again for subsequent studies so we will visit their place of work to gauge their interest in acting as PPE trainers. We plan to recruit up to 10 healers who report using PPE effectively at every vaccination event.

Health care workers from the target community will be recruited if they provide primary care or HIV/TB services in the primary health care facility. A list of eligible providers will be elicited from the facility chief; one meeting to discuss the study will be held in the clinic. If the health care worker is interested in participating, they will be consented by a study assistant at the health facility or in a location of their preference. A letter of support for this study from the Provincial Department of Health is attached.

Participant Confidentiality

The study will be conducted according to national and international standards of research ethics, to ensure that the rights of all participants will be respected. Ethical approval from the Wits Human Research Ethics Committee (Medical), the Mpumalanga Provincial Research Committee, and of the Faculty of Medicine at Vanderbilt University will be obtained before any data collection activity commences.

The involvement of individuals in the interviews will be strictly voluntary. After introducing him/herself, the interviewer will read the informed consent to the participant and answer any questions they may have. If he/she does not accept, the discussion with the interview will end. The participants will be assured of the utmost confidentiality on the part of the teams involved in the study.

Information regarding consent will not be logged anywhere and signed forms will be stored in a locked cabinet separate from transcripts and other potentially identifying information from the study. Only the principal investigators will have access signed consent forms. Transcripts will also be maintained to ensure confidentiality and access is restricted to authorized investigators. The confidentiality of the information collected will be strictly guarded.

Adverse Events

The proposed research will establish the following data and safety monitoring procedures, in compliance with NIH requirements, to ensure participant safety and protect the validity and integrity of data. The study is low risk, with intervention content focusing on providing personal protective equipment to rural South African traditional healers. However, we acknowledge that

the participant population is vulnerable and given that the focus of the research is on HIV, a stigmatized condition, the following safety plan will be implemented.

[name] will be primarily responsible for monitoring the proposed study. Together Drs. [name] and [name] (Wits), will meet regularly with the site study coordinator and research team to discuss and resolve any situations arising that relate to ethics or human subjects protection. Together with MRC/Wits Agincourt Research Unit senior field staff, they will devise and implement an appropriate remedial course of action that sufficiently addresses any critical incident or adverse event that arises. [name] will promptly inform the VU IRB, while [name] will inform the Wits HREC and Mpumalanga Province research ethics committee of any event that occurs.

